8.11. Occupational Exposure

An occupational exposure occurs when, during the performance of job duties, a person (whether a healthcare professional or otherwise) gets in unplanned direct contact with the product, which may or may not lead to the occurrence of an AE.

An occupational exposure is reported to the drug safety unit within 24 hours of the investigator's awareness, using the SAE report form, regardless of whether there is an associated AE/SAE. Since the information does not pertain to a patient enrolled in the study, the information is not reported on a CRF; however, a copy of the completed SAE report form is maintained in the investigator site file.

8.12. Withdrawal Due to Adverse Events (See Also the Section on [Patient Withdrawal](#))

Withdrawal due to AEs should be distinguished from withdrawal due to other causes, according to the definition of AE noted earlier, and recorded on the appropriate AE CRF page.

When a patient withdraws because of an SAE, the SAE must be reported in accordance with the reporting requirements defined below.

8.13. Eliciting Adverse Event Information

The investigator is to report all directly observed AEs and all AEs spontaneously reported by the study patient. In addition, each study patient will be questioned about AEs.

8.14. Reporting Requirements

Each AE is to be assessed to determine if it meets the criteria for SAEs. If an SAE occurs, expedited reporting will follow local and international regulations, as appropriate.

8.14.1. Serious Adverse Event Reporting Requirements

If an SAE occurs, Pfizer is to be notified within 24 hours of investigator awareness of the event. In particular, if the SAE is fatal or life-threatening, notification to Pfizer must be made immediately, irrespective of the extent of available AE information. This time frame also applies to additional new information (follow-up) on previously forwarded SAE reports as well as to the initial and follow-up reporting of EDP, exposure via breastfeeding, and occupational exposure cases.

In the rare event that the investigator does not become aware of the occurrence of an SAE immediately (eg, if an outpatient study patient initially seeks treatment elsewhere), the investigator is to report the event within 24 hours after learning of it and document the time of his or her first awareness of the AE.

For all SAEs, the investigator is obligated to pursue and provide information to Pfizer in accordance with the time frames for reporting specified above. In addition, an investigator may be requested by Pfizer to obtain specific additional follow-up information in an expedited fashion. This information collected for SAEs is more detailed than that captured

on the AE CRF. In general, this will include a description of the AE in sufficient detail to allow for a complete medical assessment of the case and independent determination of possible causality. Information on other possible causes of the event, such as concomitant medications, vaccines, and/or illnesses, must be provided. In the case of a patient death, a summary of available autopsy findings must be submitted as soon as possible to Pfizer or its designated representative.

8.14.2. Non-Serious Adverse Event Reporting Requirements

All AEs will be reported on the AE page(s) of the CRF. It should be noted that the form for collection of SAE information is not the same as the AE CRF. Where the same data are collected, the forms must be completed in a consistent manner. For example, the same AE term should be used on both forms. AEs should be reported using concise medical terminology on the CRFs as well as on the form for collection of SAE information.

8.14.3. Sponsor's Reporting Requirements to Regulatory Authorities

AE reporting, including suspected unexpected serious adverse reactions, will be carried out in accordance with applicable local regulations.

9. DATA ANALYSIS/STATISTICAL METHODS

Additional details of the analyses will be provided in the statistical analysis plan (SAP) and the clinical study report (CSR), which will be maintained by Pfizer. This document may modify the plans outlined in the protocol; however, any major modifications of the preliminary endpoint definition and/or its analysis will also be reflected in a protocol amendment.

The information may include details of missing and, if applicable, unused and spurious data. Deviations from the statistical plan will be reported in the clinical study report.

9.1. Analysis Sets

Data analysis will be performed on the following analysis populations:

1. Safety analysis set.
 - The safety analysis set includes all enrolled patients who receive at least one dose of study treatment.
2. Full analysis set.
 - The full analysis set includes all enrolled patients.

3. Per-protocol analysis set (evaluable for MTD).

- The per protocol analysis set includes all enrolled patients who receive at least one dose of study treatment and who do not have major treatment deviations during first cycle. Patients with major treatment deviations during the first cycle of treatment are not evaluable for the MTD assessment and will be replaced as needed to permit MTD estimation. Major treatment deviations include failure to satisfy major entry criteria (eg, confirmation of the target disease; signed informed consent) or use of other anticancer treatments during the active treatment and disease follow-up phases other than as defined/allowed in this protocol.

[figure not shown]
4. Modified Intent-to-Treat (mITT) Population.

- The modified intent-to-treat (mITT) is the analysis population that will follow the ITT principle and include patients receiving at least 1 dose of study medication with baseline assessment and at least 1 post baseline assessment, disease progression, or death before the first tumor assessment. The mITT population may be used for interim analysis and conference presentations when the study is still ongoing.

5. PK analysis sets.

- The PK parameter analysis population is defined as all enrolled patients treated who have sufficient information to estimate at least 1 of the PK parameters of interest and who have no major protocol deviations influencing the PK assessment.

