In addition, observation of a confirmed CRS event that meets the above qualifications following later infusions (ie, after Cycle 1 Day 1) or CRS events that are approaching the limit of tolerability may prompt the investigators and sponsor to include evaluation of a Dose Prime for subsequent cohorts.

After confirmation of the safety of Dose Prime, the treatment schedule will implement the inclusion of the fixed priming dose as the first dose (C1D1) followed by a second dose (C1D8) that will continue to be escalated in subsequent cohorts following an mTPI method in cohorts of 2-4 patients. After the MTD has been established, the priming dose may potentially be further verified in connection to the established MTD/RP2D, including consideration of more than one priming step, if indicated, using information from all patients who were included in the initial priming dose determination as well as those enrolled in subsequent dosing cohorts.

The primary DLT observation period for cohorts that include Dose Prime will be 21 days following the first dose (C1D1). The dose escalation should a Dose Prime be instituted is depicted in Figure 4.

For cohorts instituting a Dose Prime, there will be a 72 hour observation period between the first dose administered to each of the initial patients enrolled (ie, patients contributing to initial DLT evaluation) at a new dose level. In addition to in-patient observation following the C1D1 dose, patients enrolled in cohorts instituting a Dose Prime must also undergo in-patient observation for at least 24 hours (for cohorts where PF-06671008 will be administered IV) or 48 hours (for cohorts where PF-06671008 will be administered SC) following the C1D8 dose.

Figure 4. Study Schematic Should Dose Prime Be Explored

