3.2.2. Criteria for Dose Escalation

The study has been designed to establish the MTD defined as the dose that yields approximately 27.5% probability of DLT and considers equivalent doses that yield probability of DLT in the interval (Equivalence Interval) 22.5% to 32.5%.

Typically patients will be enrolled in cohorts of 2 to 4, but patients could be initially enrolled in cohorts of 1-2 for the lower doses (see section [Dose Escalation Phase \(Part 1\)](#)). The initial 2-4 patients to be included in a cohort will be open to any of the tumor types outlined in [Appendix 2](#). When required to expand a cohort for further evaluation of the MTD, enrollment of patients may be limited to those with NSCLC, SCCHN, CRC or TNBC.

For IV administration cohorts, initial dose levels are provided in [Table 1](#) and will be followed if no DLTs are observed; intermediate doses may be evaluated based on clinical findings. Subsequent maximum dose increases will be a maximum of 2-fold (100%) if no DLTs are observed. For SC administration cohorts, during the initial dose escalation levels, maximum dose increases will be up to 3-fold if no DLTs or safety events that are approaching the limit of tolerability are observed. The initial dose to be evaluated for SC administration will be equal to the dose level selected as the IV Dose Prime. The evaluation of the IV and SC routes of administration will proceed through dose escalation independently according to the mTPI method. Once the first DLT is observed, the maximum increase would follow a modified Fibonacci series in case of dose escalation (ie, 67%, 50%, 33%, etc.). Patients will be assigned to a dose that is closest to the current MTD prediction based on the mTPI method. The mTPI method relies upon a statistical probability algorithm, calculated using all patients treated in prior and current cohorts at the same dose level to determine (Decision Rules) where future cohorts should involve dose escalation, no change in dose, or dose de-escalation as presented in [Table 2](#) (see also Section [Statistical Methods and Properties](#)).

Table 1. Dose Escalation Levels for IV Administration

Dose Level	Dose (ng/kg)
1 (Starting Dose)	1.5
2	7.5
3	20
4	50
5	100
6	200
7	300
8	400

* Intermediate doses may be evaluated based on clinical findings (eg, a dose between 20 and 50 ng/kg).

Table 2. Decision Rules

Number of Patients Having DLT	Number of Patient Treated at a Dose Level										

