3.3. DLT Definition

Severity of adverse events will be graded according to CTCAE version 4.03 ([Appendix 6](#)). For the purpose of dose escalation, any of the following adverse events occurring in the first cycle of treatment (21 days after the first dose) will be classified as DLTs, unless there is a clear alternative explanation (eg, related to underlying disease/progression):

Hematologic:

- Grade 4 neutropenia lasting ≥ 5 days;
- Febrile neutropenia defined as an absolute neutrophil count (ANC) $<1.0 \times 10^9/L$ with a single temperature of $>38.3^{\circ}\text{C}$, or 101°F , or a sustained temperature of $\geq 38^{\circ}\text{C}$, or 100.4°F , for more than one hour;
- Grade ≥ 3 neutropenia with infection;
- Grade 3 thrombocytopenia with Grade ≥ 2 bleeding;

- Grade 4 thrombocytopenia.

Non-hematologic:

- Grade 4 toxicities (not attributed to CRS) that are considered clinically significant;
- Grade 3 toxicities (not attributed to CRS) that are considered clinically significant despite maximal supportive care (eg, nausea, vomiting, diarrhea, easily corrected electrolyte abnormalities) that last >72 hours;
- Grade ≥ 3 CRS considered not to be due to an IRR, allergic reaction or anaphylaxis, except those i) not maximally treated or ii) events that are maximally treated, (eg, including the use of tocilizumab and/or vasopressors), and resolve to \leq Grade 2 within 72 hours;
- Delay by more than 2 weeks in receiving the next scheduled dose due to persisting treatment related toxicities.

In addition, clinically important or persistent toxicities that are not included in the above criteria may be considered a DLT following review by the sponsor and the investigators.

Grade 3 infusion reaction, allergic reaction or anaphylaxis will not be considered as DLTs but may be a reason for study discontinuation and should be reviewed with the sponsor.

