3.4. MTD Definition

The estimated MTD is the dose level associated with approximately 27.5% of DLT-evaluable patients experiencing a DLT. The target interval for the DLT rate is (22.5%-32.5%). Due to the discreteness of the dose levels and in the interest of the safety of patients, the estimated MTD is the highest tested dose level with DLT rate ≤ 0.325 in at least 6-12 evaluable patients for DLT. The study aims to determine a MTD for a dose regimen that does not include a priming dose administered IV, and an independent MTD for an IV dose regimen that includes a priming dose. In addition, the study aims to determine a MTD for PF-06671008 administered SC and may also determine an independent MTD for a SC dose regimen that includes a priming dose.

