5.4.6. Dosing Interruptions

Patients experiencing Grade 3 or 4 potentially treatment related toxicity or intolerable Grade 2 toxicity despite supportive care should have their treatment interrupted.

Appropriate follow up assessments should be done until adequate recovery occurs as assessed by the investigator. Criteria required before treatment can resume are described in the [Dose Delays](#) section.

Doses may be held as needed until toxicity resolution. Depending on when the AE resolved, a treatment interruption may lead to the patient missing all subsequent planned doses within that same cycle or even to delay the initiation of the subsequent cycle.

If the adverse event that led to the treatment interruption recovers within the same cycle, then re-dosing in that cycle is allowed. Doses omitted for toxicity are not replaced within the same cycle. The need for a dose reduction at the time of treatment resumption should be based on the criteria defined in the [Dose Reductions](#) section, unless expressly agreed otherwise following discussion between the investigator and the sponsor.

In the event of a treatment interruption for reasons other than treatment-related toxicity (eg, elective surgery) lasting >2 weeks, treatment resumption will be decided in consultation with the sponsor.

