#### 2.2.4. MTD Definition

*The estimated MTD is the dose level associated with approximately 27.5% of DLT-evaluable patients experiencing a DLT. The target interval for the DLT rate is (22.5%-32.5%). Due to the discreteness of the dose levels and in the interest of the safety of patients, the estimated MTD is the highest tested dose level with DLT rate  $\leq 0.325$  in at least 6-12 DLT evaluable patients for DLT. The study aims to determine a MTD for a dose regimen that does not include a priming dose administered IV, and an independent MTD for an IV dose regimen that includes a priming dose. In addition, the study aims to determine a MTD for PF-06671008 administered SC and may also determine an independent MTD for a SC dose regimen that includes a priming dose.*

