##### 4.3. 'PER PROTOCOL' Analysis Set (Part 1)

[figure not shown]
The per protocol analysis set includes all enrolled patients who receive at least one dose of study treatment and who do not have major treatment deviations during the first cycle. Patients with major treatment deviations during the first cycle of treatment are not evaluable for the MTD assessment and will be replaced as needed to permit MTD estimation. Major treatment deviations include failure to satisfy major entry criteria (eg, confirmation of the target disease; signed informed consent) or use of other anticancer treatments during the active treatment and disease follow-up phases other than as defined/allowed in this protocol.

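### The set labelled evaluable for MTD does not require a patient without a DLT to be observed for 21 days or, in Dose Prime cohorts, to have received the escalated dose

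*Protocol*

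**What the plan says.** **Membership.** Protocol 9.1 labels the per-protocol set as evaluable for MTD and says it "includes all enrolled patients who receive at least one dose of study treatment and who do not have major treatment deviations during first cycle". SAP 4.3 repeats this for patients "who receive at least one dose of study treatment and who do not have major treatment deviations during the first cycle". The examples of a major treatment deviation are failing major entry criteria and using other anticancer treatment. Patients with such deviations are non-evaluable and are replaced as needed. SAP 6.2.1 summarises DLTs, the Part 1 primary endpoint, in this set.

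**Window.** Protocol 3.3 counts DLTs in the first cycle, glossed as 21 days after the first dose. For Dose Prime cohorts, section 3.2.1 keeps the same clock: "The primary DLT observation period for cohorts that include Dose Prime will be 21 days following the first dose (C1D1"). In those cohorts the escalated dose is first given on C1D8.

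**Other denominators.** Protocol 3.2.2 says the mTPI algorithm is "calculated using all patients treated in prior and current cohorts at the same dose level to determine (Decision Rules") whether the next cohort escalates, stays or de-escalates. Protocol 3.4 states: "The estimated MTD is the dose level associated with approximately 27.5% of DLT-evaluable patients experiencing a DLT". SAP 2.2.4 asks for a DLT rate of at most 0.325 "in at least 6-12 DLT evaluable patients for DLT". No section says that DLT-evaluable means the per-protocol set.

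**Later exclusions.** SAP 4.8 promises a full list of deviations that exclude a patient from the per-protocol analysis, to be settled before database release.

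**The concern.** A patient without a DLT is informative only to the extent that the risk period was observed. The written rule asks for one dose and no major deviation. It therefore lets in two kinds of patient who carry little or no information on the dose being tested:

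- a patient lost to follow-up, withdrawn or dead of a non-toxic cause before Day 21;
- in a Dose Prime cohort, a patient who had the priming dose but never the escalated one.

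Counting either as a full non-DLT lowers the observed DLT rate. It also fills one of the places in the minimum of six evaluable patients needed to declare an MTD. The error is always in the less cautious direction, and it enters the denominator of the primary endpoint in a first-in-patient escalation.

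**Working it through.** **1. The plan's own figure.** The evaluability rule has no stated figure. The nearest is the escalation-probability table in protocol 9.2 and SAP 5.2.1, which assumes escalation on 0/3 or 1/6:

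Pr(escalate) = (1−p)³ + 3p(1−p)²·(1−p)³.

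At p = 0.40 this is 0.216 + 0.432 × 0.216 = 0.309, printed as 0.31. All nine printed values reproduce. The formula treats every patient as fully observed. So do the Appendix 7 simulations, which assume the next cohort enrols once the previous cohort's DLT responses are in.

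**2. Effect on the printed decision rules.** Take each cell with x DLTs in n patients, for n = 2 to 11 and x = 1 to 7 with x ≤ n. The number of cells is 2+3+4+5+6+7+7+7+7+7 = 55. Add one patient counted as a non-DLT and compare x/n with x/(n+1).

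| Source | Next dose action less cautious | Only U to D |
|---|---|---|
| Protocol Table 2 | 1/5, 2/3, 2/9, 3/6, 4/10 | 2/2, 3/4, 4/7, 5/8 |
| SAP Table 2 | 1/5, 2/3, 2/9, 3/6, 4/9 | 2/2, 3/4, 4/6, 5/8 |
| Appendix 7 | 1/5, 2/3, 2/10, 3/6, 4/10 | 2/2, 3/4, 4/7, 5/9 |

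Each source has 5 cells where the action changes and 4 that go only from U to D. Both U and D de-escalate; they differ in whether the dose may be revisited. Three action changes are common to all sources:

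- 1/5 Stay becomes 1/6 Escalate;
- 2/3 De-escalate becomes 2/4 Stay;
- 3/6 De-escalate becomes 3/7 Stay.

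**3. Effect at the 0.325 cap.** 2/6 = 33.3% cannot be selected as MTD; 2/7 = 28.6% can. Likewise 3/9 = 33.3% becomes 3/10 = 30.0%.

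**4. Size for one wholly unobserved patient.** Let p be the true DLT rate. These are fixed-n binomial tails.

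*At most 1 DLT in n = 6 (Escalate).* Counted: five observed, Pr(Bin(5,p) ≤ 1). Replaced: Pr(Bin(6,p) ≤ 1).
- p = 0.40: counted 0.0778 + 0.2592 = 0.337; replaced 0.0467 + 0.1866 = 0.233.
- p = 0.275: 0.580 and 0.476.

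*Rate at or below 0.325 in n = 7 (at most 2 DLTs).* Counted: six observed, Pr(Bin(6,p) ≤ 2). Replaced: Pr(Bin(7,p) ≤ 2).
- p = 0.40: 0.544 and 0.420.
- p = 0.275: 0.789 and 0.703.

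**The case against.** **The deviation list is open, and other controls exist.** The examples are introduced by *include*, SAP 4.8 promises a full list, and protocol 9.7 has sponsor and investigators reviewing each dose level continuously. This stands as a mitigation. But the SAP 4.8 list is due only before database release, and no section ties it to dose decisions taken earlier.

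**Most early stoppers are covered.** Patients who merely stop drug are followed for adverse events for 28 days after the last dose, and starting other anticancer therapy in Cycle 1 is already a named deviation. This stands, and it narrows the issue to loss, withdrawal of consent, non-toxic death and a missed escalated dose.

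**A reader might infer that DLT-evaluable has no meaning, or that 3.2.2 contradicts 9.1.** The documents do not support either firmly. The label in 9.1 and SAP 6.2.1 suggest that DLT-evaluable is the per-protocol set under another name. Section 3.2.2 pools patients treated at the same dose level, so it may already leave out a primed patient who never had the escalated dose. What remains is that no text makes these links.

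**A reader might infer that a permitted delay can leave no observation after the escalated dose.** Dosing is interrupted for "intolerable Grade 2 toxicity despite supportive care should have their treatment interrupted" and may resume within 14 days. The related DLT criterion is "Delay by more than 2 weeks in receiving the next scheduled dose due to persisting treatment related toxicities". If a C1D8 dose simply shifts by d days and the window stays fixed, 21 − (7 + d) = 14 − d days remain: 14, 7 or 0 for d = 0, 7 or 14. That depends on an unsettled reading. Protocol 3.1 and 5.4.7 run a delayed cycle to the 4th dose, and the endpoint is first-cycle DLTs. Section 5.4.6 says doses omitted for toxicity are not made up within the cycle. The Administration text in 5.4 is redacted and the Dose Prime schematic is not shown. The passages conflict, but zero observation is not an established consequence.

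**The size can be overstated.** Quoting 9 of 55 cells would include the four that still de-escalate. Comparing with a patient dropped and not replaced would widen the spread, but 9.1 replaces non-evaluable patients. Also, 2/6 and 2/7 are both Stay, so the cap example matters only when the MTD is declared.

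**Conclusion.** The point holds in limited form. The written rule admits patients without a DLT whose window was not observed and, on its face, Dose Prime patients who never received the tested dose. No text available at a dose decision excludes or replaces them.

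One such patient makes the next action less cautious in 5 of 55 cells in each printed version of the rules. At a true DLT rate of 40%, the two illustrative probabilities are 0.34 against 0.23 and 0.54 against 0.42.

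These figures assume exactly one wholly unobserved patient, independent DLTs at a common rate and a fixed n. They are not operating characteristics of the design, because paths such as 0/3 would already have escalated. The documents give no loss rate, so the expected effect over the trial cannot be stated. A partly observed patient would have a smaller effect. The Dose Prime part applies only if a priming dose is adopted.

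This should be fixed, because it concerns the primary denominator and costs little. The documents do not show that dose decisions were in fact biased.

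**What to change.** In protocol 9.1 and SAP 4.3, define DLT-evaluable once:

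- (a) any patient with a DLT in the window; or
- (b) a patient without a DLT who was observed to the end of the window and, in a Dose Prime cohort, received the escalated dose.

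Replace other patients under the existing 9.1 mechanism. Use this one set for the counts entering Table 2 and Appendix 7 at each dose decision, for the MTD definition (protocol 3.4, SAP 2.2.4) and for the SAP 6.2.1 summary.

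Separately, reconcile the 21-days-after-first-dose window (protocol 3.2.1, 3.3) with a delayed Cycle 1 that runs to the 4th dose (3.1, 5.4.7) and with the statement on omitted doses (5.4.6). The observation due after a delayed escalated dose should then have one reading. Which reading applies is for the sponsor to decide. Patients should not become non-evaluable merely because toxicity delayed a dose, since that would remove informative tolerability data.

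The cost is one definition, aligned wording in the sections named, and an occasional replacement patient with the added 21-day observation. Non-evaluable patients who were dosed stay in the safety analysis set.
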